### 5.4.2 Biomicroscopy Findings/Slit Lamp Examination

A slit-lamp examination will be performed at the screening, 1 day, 1 week, and 1 month visits to evaluate the anterior segment of the eye, including eyelids/conjunctiva, cornea, lens, and iris/anterior chamber.

A summary of grading at each visit for corneal edema, aqueous cells, and aqueous flare will be presented. Cataract grading and cataract type will be presented for the screening visit. A listing with this information, plus details on any abnormal slit lamp findings, will be provided. Additionally, a listing of postoperative IOL observations will be created.

### 5.4.3 Intraocular Pressure

Intraocular pressure (IOP) measurements will be recorded in mmHg and rounded to the nearest whole mmHg. IOP measurements will be conducted at the screening, 1 day, 1 week, and 1 month visits.

Descriptive summaries (count, mean, median, standard deviation, minimum and maximum) of observed values will be presented at each study visit and for the change at 1 month from baseline. A listing will supplement the summary table.

#### 5.4.4 Dilated Fundus Examination

The dilated fundus examination will be conducted at the screening and 1 month visits. The examination will be performed to evaluate the health of the vitreous, retina, macula, choroid, and optic nerve. A listing of fundus findings will delineate the results.

[figure not shown]
### 6 SAMPLE SIZE AND POWER CALCULATIONS

Based on a sample of 100 surgeries, the expected half-width of the 95% confidence interval for the percentage of surgeons reporting ‘Yes’ to the question “***Did UNITY VCS using anterior segment surgical functionality perform per the intended use as defined in Protocol Section 5.1?***” will be  $1.96 \cdot \sqrt{p(1-p)/100}$ . This half-width is widest at  $p = 50\%$ . Under this conservative assumption, the expected half-width is <10% given the sample size of 100.

Allow enrollment for an additional 10% for screen failure and 10% for lost to follow-up to ensure 100 completed subjects. (See also Section 8 of the protocol for more details.)

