	

• Diagnosed with severe systemic (e.g., history of cerebral vascular accident) or retinal disorders (e.g., macular degeneration, diabetic retinopathy, or other retinal pathology that might limit postoperative visual acuity or predispose the subject to postoperative retinal complications) in the operative eye

• A poorly dilating pupil or other pupil defect that prevents the iris from retracting peripherally to at least 6 mm diameter dilation in the operative eye

Data analysis and sample size justification	
The primary analysis set for effectiveness outcomes will be the all-implanted analysis set. The all-implanted analysis set includes all eyes with successful completion of the cataract surgery including IOL implantation. The safety analysis set will include all eyes with attempted use of the UNITY VCS (successful or aborted after contact with the eye) and will be used for the safety outcomes. Attempted use of the UNITY VCS is defined as any time the device makes contact with the eye.
 
There will be no hypothesis testing for any study outcome. All study outcomes will be presented as data listings or with summary statistics that are appropriate to the scale of the endpoint (continuous, dichotomous, etc.).
 
Based on a sample of 100 subjects, the expected half-width of the 95 % confidence interval for the percentage of surgeons reporting 'yes' to the question "Did UNITY VCS using anterior segment surgical functionality perform per the intended use as defined in Protocol Section 5.1?" will be <math>1.96 \cdot \sqrt{(p(1-p)/100)}</math>. This half-width is widest at <math>p = 50\%</math>. Under this conservative assumption, the expected half-width is <10% given the sample size of 100.
 
Allow enrollment for an additional 10% for screen failure and 10% for lost to follow-up to ensure 100 completed subjects.

**Table 3–1** Schedule of Study Procedures and Assessments

Visit	Visit 0 Screening	Visit 00 Surgery	Visit 1 1 Day	Visit 2 1 Week	Visit 3 1 Month / Exit	Early Exit	Unscheduled Visit 
Day Number	Day -60 to 0	Day 0	Day 1 to 3	Day 4 to 10	Day 28 to 42	N/A	N/A
Eye	Both Eyes	Study eye	Study eye	Study eye	Study eye	Study eye	Study eye
Informed Consent	X						
Demographics	X						
Medical and Ocular History	X						
Concomitant Medications	X	X	X	X	X	X	X
Inclusion/Exclusion	X						

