## 8 STUDY POPULATION

The study population will consist of male and female subjects (over the age of 18 years) with a diagnosis of age-related noncomplicated cataract (unilaterally). It is aimed to enroll (consent) approximately 120 subjects in up to 5 sites in the United States and/or Australia with a target of 100 subjects treated, with 10 to 40 subjects per site. Site-specific targets may vary based upon individual site capabilities and each site may include more than one surgeon. Each surgeon will perform at least 10 surgeries, but no more than 33% of the total subjects treated. Estimated time needed to recruit subjects for the study is approximately 5 months; however, unanticipated circumstances may shorten or lengthen this time and would not require amendment of this protocol. Because a 10% screening failure rate is expected and 10% for lost to follow-up, approximately 120 subjects are expected to be enrolled to ensure 100 completed subjects.

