#### 12.4.1.2 Analysis Methods

Standard descriptive statistics will be presented for the primary effectiveness endpoint based on the type. For categorical summaries, statistics will include sample size, number in category, and percentage in each category. For continuous summaries, number of subjects, mean, median, standard deviation, minimum, maximum, and two-sided 95% confidence intervals for both mean and median will be reported. Individual subject data listings will also be provided.

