### 4.2 Effectiveness Hypotheses

No hypothesis testing will be performed. Analyses will be descriptive only.

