#### 4.3.1 Analysis of the Primary Endpoint

After each surgery, the surgeon completes a user preference questionnaire. For subjects in the all-implanted analysis set, the rate of 'Yes' responses to the question ***Did UNITY VCS using anterior segment surgical functionality perform per the intended use as defined in Protocol Section 5.1?*** will be presented with a count and percentage and will be accompanied by a two-sided exact binomial 95% confidence interval.

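### SAP section 6 promises a 95% half-width under 10 points at p = 50% and n = 100, but the exact interval planned in SAP section 4.3.1 gives about 10.1 points

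*SAP*

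**What the plan says.** SAP section 6 sets out the precision argument: "Based on a sample of 100 surgeries, the expected half-width of the 95% confidence interval" for the primary endpoint will be 1.96·√(p(1−p)/100). It continues, "This half-width is widest at" p = 50%, and concludes: "Under this conservative assumption, the expected half-width is <10% given the sample size of 100". Protocol section 12.8 gives the same argument. So does the protocol summary (section 3), which begins: "Based on a sample of 100 subjects, the expected half-width of the 95 % confidence interval for the percentage of surgeons reporting".

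For the analysis of the same endpoint, SAP section 4.3.1 says that the rate of 'Yes' responses "will be presented with a count and percentage and will be accompanied by a two-sided exact binomial 95% confidence interval". Protocol section 12.4.1.2 names no interval for a categorical endpoint: "For categorical summaries, statistics will include sample size, number in category, and percentage in each category". SAP section 4.3.1 is thus the only place that specifies the interval to be reported.

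SAP section 4.2 rules out testing: "No hypothesis testing will be performed. Analyses will be descriptive only".

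**The concern.** The planning formula is the half-width of a normal-approximation (Wald) interval. The interval to be reported is an exact binomial one, which is wider. Neither document calls the formula an approximation to the exact interval; the text says that the half-width will be the formula, and then gives a strict upper bound. At 9.80 points the formula sits so close to 10 that the change of method could carry the result across the bound.

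No hypothesis is tested, so this is the only precision figure offered to justify the sample size. Anyone who recomputes it with the method of SAP section 4.3.1 should find that it holds in the stated worst case.

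**Working it through.** **Inputs**

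- n = 100 surgeries; planning rate p = 50%; formula 1.96·√(p(1−p)/100); stated result under 10% (SAP section 6).
- Two-sided exact binomial 95% interval, hence 2.5% per tail (SAP section 4.3.1).
- Assumption: exact binomial means Clopper-Pearson. The SAP does not name the method; this is the usual reading.

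**Step 1. The plan's own figure.** 1.96·√(0.5 × 0.5/100) = 1.96 × 0.05 = 0.0980, or 9.80 points. The statement that this is under 10% is reproduced.

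**Step 2. The planned interval.** For x 'Yes' answers out of n, the Clopper-Pearson limits are

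- lower: the 0.025 quantile of Beta(x, n−x+1), or 0 if x = 0;
- upper: the 0.975 quantile of Beta(x+1, n−x), or 1 if x = n.

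The half-width is (upper − lower)/2. Its expected value is the average over x from Binomial(n, p).

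- Expected half-width at p = 50%, n = 100: **10.12 points**.
- At exactly 50/100 the limits are 39.83% and 60.17%, so the half-width is **10.17 points**, the largest for any count.

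**Step 3. Where the bound fails at n = 100**

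- By observed count: the half-width is 10 points or more for 41 to 59 'Yes' (59/100: 10.01; 60/100: 9.97). If the true rate is 50%, these counts have a probability of about 94%.
- By true rate: the expected half-width is 10 points or more for p from about 42.2% to 57.8% (grid step 0.1 points).

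**Step 4. Size of the gap across rates (n = 100)**

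| True p | Formula (points) | Expected exact half-width (points) |
|---|---|---|
| 50% | 9.80 | 10.12 |
| 80% | 7.84 | 8.20 |
| 90% | 5.88 | 6.28 |
| 95% | 4.27 | 4.71 |

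The formula is 0.3 to 0.4 points too favourable throughout the table, but it crosses 10 only near p = 50%.

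**Step 5. Sample size at which the bound would hold for the exact interval at p = 50%**

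| n | Expected half-width (points) | Largest half-width over all counts (points) |
|---|---|---|
| 100 | 10.12 | 10.17 |
| 102 | 10.02 | 10.07 |
| 103 | 9.97 | 10.01 |
| 104 | 9.92 | 9.97 |
| 108 | 9.73 | 9.78 |

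The bound holds in expectation from n = 103, and for every possible count from n = 104. The last row is the case in which 120 are enrolled, 10% fail screening (120 × 0.9 = 108), and all the rest are treated and have an answer recorded.

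**The case against.** **The sentence is true of the formula it follows.** SAP section 6 prints the formula, says where it is widest, and then gives the bound. Planning with a normal approximation and reporting an exact interval is common practice, and on this view only a label is missing. This stands in part: there is no calculation error, and labelling the formula would remove the contradiction. But without a label the text asserts the half-width of the interval for this endpoint, and the interval specified elsewhere in the SAP does not meet the bound.

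**The result depends on which exact interval is meant.** At p = 50% and n = 100, a mid-P interval has an expected half-width of 9.68 points and Blaker's exact interval about 9.88 (10.05 at 50/100). This is correct. The SAP names neither, and Clopper-Pearson is the usual reading. If another method is intended, SAP section 4.3.1 should name it.

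**More than 100 eyes may be analysed.** Protocol section 8 says: "Because a 10% screening failure rate is expected and 10% for lost to follow-up, approximately 120 subjects are expected to be enrolled". With 108 answers the bound would hold. SAP section 6, however, ties its figure to 100.

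**The refinement is finer than other uncertainty in the figure.** Either half-width assumes 100 independent answers, whereas each surgeon performs at least 10 surgeries and up to 33% of the total (protocol section 8). The documents give no correlation. As an illustration, with 25 surgeries per surgeon and an intraclass correlation of 0.005 to 0.01, the formula value becomes 9.80·√(1 + 24 × 0.005) = 10.4 to 9.80·√(1 + 24 × 0.01) = 10.9 points. This is fair, and it limits how much weight the second digit can bear. It is a further reason not to claim a strict bound of 10.

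**The protocol is not inconsistent in itself.** This is also correct. Protocol section 12.4.1.2 names no interval, so the mismatch lies between two sections of the SAP. The protocol needs the change only to keep the two documents aligned.

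**Conclusion.** The point holds. The SAP states an expected half-width under 10 points at p = 50% and n = 100, and the interval it plans to report has an expected half-width of 10.12 points there (at most 10.17). This is a mismatch between the planning formula and the reported interval. It rests on reading exact binomial as Clopper-Pearson, on n = 100 as stated, and on independent answers.

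Its weight is low. The excess over the bound is 0.12 points in expectation and 0.17 at most. It is confined to true rates near 50%; at the high rates one would hope for with this endpoint, both figures are far below 10. No success threshold or decision is tied to 10%, and the sample size need not change. The sentence should still be corrected, because it is the only precision figure behind the sample size and the correction is simple.

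**What to change.** In SAP section 6, replace the closing statement on precision with wording such as:

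> With 100 surgeries and the two-sided exact binomial (Clopper-Pearson) 95% interval, the expected half-width is about 10.1 percentage points at p = 50% (10.2 at an observed 50/100).

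Name the method in SAP section 4.3.1 in the same way. If the formula is kept, label it a normal approximation. Carry the sentence into protocol sections 3 and 12.8 at the next amendment; it does not warrant an amendment of its own.

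Optionally, add the exact limits at high rates, which are more informative for this endpoint: 88.7% to 98.4% at 95/100, and a lower limit of 96.4% at 100/100.

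The same edit can correct a slip of wording. The precision text speaks of a percentage of surgeons, but the questionnaire is completed after each surgery (SAP section 4.1), so it should read surgeries.

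The cost is one sentence in each of three places and a slightly less favourable stated figure. The sample size does not change, and nor does the analysis under the Clopper-Pearson reading.

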### 8 REVISION HISTORY

This is the original (Version 1.0) Statistical Analysis Plan for this study. This version of the Statistical Analysis Plan is based on Version 1.0 of the study protocol.

## 9 APPENDIX

**Table 9–1** **Schedule of Study Procedures and Assessments**

Visit	Visit 0 Screening	Visit 00 Surgery■	Visit 1 1 Day	Visit 2 1 Week	Visit 3 1 Month / Exit	Early Exit	Unscheduled Visit 
Day Number	Day -60 to 0	Day 0	Day 1 to 3	Day 4 to 10	Day 28 to 42	N/A	N/A
Eye	Both Eyes	Study eye	Study eye	Study eye	Study eye	Study eye	Study eye
Informed Consent	X						
Demographics	X						
Medical and Ocular History	X						
Concomitant Medications	X	X	X	X	X	X	X
Inclusion/Exclusion	X						
Urine Pregnancy Test 1*	X						
Dilated Pupil Size	X						
Keratometry	X						
Biometry (ACD, AL)	X						
Slit Lamp Examination	X		X	X	X	X	(✓)

Visit	Visit 0 Screening	Visit 00 Surgery	Visit 1 1 Day	Visit 2 1 Week	Visit 3 1 Month / Exit	Early Exit	Unscheduled Visit 
Day Number	Day -60 to 0	Day 0	Day 1 to 3	Day 4 to 10	Day 28 to 42	N/A	N/A
Eye	Both Eyes	Study eye	Study eye	Study eye	Study eye	Study eye	Study eye
UCDVA 			X				
BCDVA 	X			X	X	X	(✓)
Intraocular Pressure	X		X	X	X	X	(✓)
Dilated Fundus Exam 	X				X	X	(✓)
Treatment (cataract surgery)		X					
Time from incision entry to incision closure		X					

Visit	Visit 0 Screening	Visit 00 Surgery 	Visit 1 1 Day	Visit 2 1 Week	Visit 3 1 Month / Exit	Early Exit	Unscheduled Visit 
Day Number	Day -60 to 0	Day 0	Day 1 to 3	Day 4 to 10	Day 28 to 42	N/A	N/A
Eye	Both Eyes	Study eye	Study eye	Study eye	Study eye	Study eye	Study eye

User Preference Questionnaire 		X					
Adverse Events	X	X	X	X	X	X	X
Device Deficiencies	X	X	X	X	X	X	X
Exit Form	(✓)	(✓)	(✓)	(✓)	X	X	(✓)

(✓) Assessment performed as necessary

 Women of child-bearing potential only

 VA to be conducted per site's SOC using Snellen chart

 VA to be conducted per site's SOC using manifest refraction and Snellen chart

 Assessment must be performed dilated

 Unscheduled Visit – additional study assessments may be performed per investigator's discretion

\* Source only entries
